11.1 Study Hypotheses

The primary objective of this study will be assessed through estimation rather than hypothesis testing, as this is a Phase I study with small sample sizes. The study includes eight subjects in each of the first three cohorts and twelve subjects in the fourth cohort.

The secondary objective of defining the multi-dose kinetics of oxfendazole will be assessed using a descriptive analysis with no formal hypothesis test. For the secondary objective of the determination of the effect of food on the kinetics of oxfendazole, equivalence between the fasting (water is permitted) and fed conditions will be tested using 90% confidence intervals and 80-125% equivalence limits for AUC_{0-∞}, AUC₀₋₂₄, and C_{max} in accordance with FDA guidance.

<http://www.fda.gov/downloads/RegulatoryInformation/Guidances/UCM126833.pdf>

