11.4.4 Pharmacokinetic Analysis

PK parameters for oxfendazole will be calculated using non-compartmental analysis. Parameters will be summarized separately by group and dose.

Maximum concentration (C_{max}), time of maximum concentration (T_{max}), and the pre-dose trough concentrations (C_{trough}) will be directly estimated from the observed concentration-time curve. Area under the curve (AUC) will be calculated using the linear up-log down trapezoidal method. λ_z will be calculated as the negative of the slope of the terminal log-linear segment of the plasma concentration-time curve. The range of data to be used for each subject and treatment will be determined by visual inspection of a semi-logarithmic plot of concentration vs. time, but will include at least three plasma concentration-time points for λ_z to be estimable. Half-life ($t_{1/2}$) will be calculated as $\ln(2)/\lambda_z$.

In Groups 1-3, $AUC_{0-\tau}$ will be calculated as AUC to the end of the 24-hour dosing interval. Oral clearance at steady state will be calculated using $AUC_{0-\tau,ss}$ after the Day 5 (expected steady state) dose as

$$CL_{ss} / F = \frac{Dose}{AUC_{0-\tau,ss}}$$

The observed accumulation ratio (AR) following multiple dosing will be estimated using the ratio of $AUC_{0-\tau}$ following multiple and single dosing. When λ_z is estimable, AR will also be estimated using λ_z calculated following multiple dosing:

$$AR = \frac{1}{1 - e^{-\lambda_z \tau}}$$

The relationship between exposure (C_{max} and AUC) and dose, i.e., dose proportionality, will be examined using ANOVA or the power model

$$P = a \times Dose^b$$

where P represents the parameter and a and b are constants. A value of b of approximately 1 indicates linear PK.

Group 4 parameters will be summarized by condition (fasting (water is permitted) or fed). In group 4, 90% confidence intervals for ratios of key exposure parameters will be estimated using appropriate analysis of variance (ANOVA) models on the log-transformed parameters. Key exposure parameters will be C_{max} , AUC to the time of the last quantifiable concentration (AUC_{0-t}), and, when λ_z is estimable, AUC extrapolated to infinity ($AUC_{0-\infty}$).

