 λ_z will be computed as the slope of a terminal region consisting of at least 3 successive points in the plot of log-transformed concentration data versus time. λ_z will be estimated using uniform weighting. Time points used in the estimation of λ_z will be initially selected using the Phoenix WinNonlin automatic algorithm. The set of points chosen must contain only timepoints after T_{max} , include at least 3 timepoints, and satisfy the Lambda Z Acceptance Criteria described above. The range of concentrations used to estimate λ_z for each profile will be inspected by the PK analyst, and the PK analyst may adjust the set of concentrations used to estimate λ_z if deemed necessary, but manually selected ranges must satisfy the same acceptance criteria as those chosen automatically by the Phoenix WinNonlin algorithm.

Drug concentrations used to calculate λ_z will be indicated in Listing 3.

 λ_z will be estimated for Doses 1 and 5 in Groups 1, 2, and 3, and for Group 4.

t½

The apparent terminal elimination half-life $(t_{1/2})$ is defined as the time required for the drug concentration to decrease by a factor of one-half in the terminal phase. The apparent terminal elimination half-life $(t_{1/2})$ will be estimated as $\ln(2)/\lambda_z$ and will be obtained from the **HL_Lambda_z** parameter calculated by Phoenix WinNonlin. $t_{1/2}$ will be estimated for Doses 1 and 5 in Groups 1, 2, and 3, and for Group 4, when λ_z is estimable.

AUC

AUC is defined as the area under the concentration-time curve. AUC will be estimated using the Linear Up Log Down calculation method.

AUC_{τ}

 AUC_{τ} is defined as AUC of a single dosing period. In groups 1-3, AUC_{τ} for a given dose will be calculated as AUC from time of dosing to the end of the 24-hour dosing interval for Dose 1 and Dose 5. AUC_{τ} will be obtained in Phoenix WinNonlin using the Partial Area functionality.

AUClast

AUC_{last} is defined as the AUC from dosing to the time of the last measured concentration \geq LLOQ (C_{last}) of that dosing period and will be obtained from the **AUClast** parameter calculated by Phoenix WinNonlin.

AUC (0-∞)

AUC $_{(0-\infty)}$ is defined as the AUC from dosing taken to the limit as the end time becomes arbitrarily large. AUC $_{(0-\infty)}$ for a given dose will be estimated by adding AUC $_{last}$ for that dose to an extrapolated value equal to the last measured concentration greater than the LLOQ divided by λ_z :

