$$AUC_{(0-\infty)} = AUC_{last} + \frac{C_{last}}{\lambda_z},$$

where C_{last} is the last measured concentration \geq LLOQ. $AUC_{(0-\infty)}$ will be obtained from the $\mathbf{AUCINF_obs}$ parameter calculated by Phoenix WinNonlin If the amount extrapolated portion of $AUC_{(0-\infty)}$ is >25%, the estimated $AUC_{(0-\infty)}$ value will be flagged when listed in the report and will be excluded from downstream statistical analyses, but included in the calculation of summary statistics.

 AUC_{τ} , will be estimated for Dose 1 and Dose 5 in Groups 1, 2, and 3. AUC_{last} will be estimated for Dose 5 in Groups 1, 2 and 3, and for Group 4. $AUC_{(0-\infty)}$ will be estimated for Group 4 when λ_z is estimable.

CL/F

For Group 4, apparent oral clearance (CL/F) will be calculated as Dose/AUC_(0- ∞) and will be obtained from the **CL_F** parameter in Phoenix WinNonlin. If the amount extrapolated portion of AUC_(0- ∞) is >25%, the estimated CL/F value will be flagged when listed in the report, but included in the calculation of summary statistics.

CLss/F

For Groups 1, 2 and 3, apparent oral clearance at steady state (CL_{SS}/F) will be calculated as the dose in mg/kg divided by the AUC_{τ} for Dose 5 (expected steady state) and will be obtained from the $Clss_F$ parameter calculated by Phoenix WinNonlin.

$$CL_{SS}/F = \frac{Dose}{AUC_{\tau, Dose 5}}$$

V_d/F

For Group 4, apparent volume of distribution (V_d/F) will be calculated as (CL/F)/ λ_z and will be obtained from the \mathbf{Vz}_F parameter in Phoenix WinNonlin. If the amount extrapolated portion of $AUC_{(0-\infty)}$ is >25%, the estimated V_d/F value will be flagged when listed in the report, but included in the calculation of summary statistics.

AR

For Groups 1, 2 and 3, the observed accumulation ratio (AR) is defined as the ratio of exposure parameters following multiple and single dosing. AR will be calculated using AUC_{τ} and C_{max} :

$$AR = \frac{AUC_{\tau, Dose 5}}{AUC_{\tau, Dose 1}},$$

$$AR = \frac{C_{\text{max, Dose 5}}}{C_{\text{max, Dose 1}}}$$

When λ_Z is estimable, AR will also be estimated using the elimination rate λz from Dose 5:

$$AR = \frac{1}{1 - e^{-\lambda_Z \tau}},$$

where τ is the length of the dosing interval, 24 hours.

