3.5.7. Analysis of Food Effect

Determination of the effect of food on the kinetics of oxfendazole in Group 4 will be conducted in accordance with current FDA guidance^{3,4}. Key exposure parameters (AUC_(0-∞), AUC_(0-last), and C_{max}) will be log-transformed and analyzed using the following mixed effects model for Y_{ijk} , the log-transformed exposure parameter observed for the *i*th condition (fed/fasted) for the *k*th subject in period *j*:

$$Y_{ijk} = \mu + \pi_j + \lambda_{d(i,j)} + \tau_{d(i,j)} + s_k + \varepsilon_{ijk}$$

where μ is an intercept; π_j is a fixed effect associated with period j; λ_i is a fixed effect associated with the condition i, $\tau_{d[i,j]}$ is a fixed effect associated with the interaction of period j and condition i; and s_{ik} is a random effect associated with the kth subject with mean 0 and variance σ_s^2 , and e_{ijk} is a random error term with mean 0 and variance σ_e^2 .

The model will be fit using REML in SAS PROC MIXED. Point estimates and 90% confidence intervals for the mean difference between fed and fasted conditions will be constructed for each log-transformed exposure parameter. SAS code will be similar to:

PROC MIXED;

CLASS PERIOD CONDITION SUBJECT;

MODEL LCMAX = PERIOD CONDITION PERIOD*CONDITION / DDFM=KR;

RANDOM SUBJECT;

LSMEANS CONDITION / ALPHA=0.1 PDIFF CL;

RUN:

Point and interval estimates of the mean difference in log-transformed exposure parameters will then be back-transformed to obtain point estimates and 90% confidence intervals for the ratio of geometric means of the parameters. Equivalence between the fasting and fed conditions will be based on whether the 90% confidence interval for the ratio of the population geometric mean of the parameter measured from the 2 conditions is contained in the interval [0.80, 1.25].

In addition, for each exposure parameter, the intrasubject coefficient of variation (CV_W) will be calculated to provide an estimate of the variability in exposure within the same subject, when the subject is administered one dose of study product on two separate occasions.

For normally distributed data with mean μ and variance σ^2 , coefficient of variation is defined as:

$$CV = \sqrt{Var\left(\frac{X - \mu}{\mu}\right)} = \frac{\sigma}{\mu} = \frac{\sqrt{Var(X)}}{E(X)}$$

If X is instead distributed log-normally (i.e., Y = log(X) is normally distributed with mean μ and variance σ^2), then:

$$E(X) = \exp\left(\mu + \frac{\sigma^2}{2}\right)$$

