| | $C_{\text{trough}}\left(\frac{\text{ng/mL}}{\text{mg/kg}}\right)$ | x.x | X.X | X.X | |
| | G, G | x.x | X.X | X.X | |
| | | X.X | X.X | X.X | |
| | $AUC_{\tau}\left(\frac{\text{ng}\cdot\text{hr/mL}}{\text{mg/kg}}\right)$ | X.X | X.X | X.X | |
| | | X.X | X.X | x.x | |
| Dose 5 | , , | X.X | X.X | x.x | |
| | $C_{\max}\left(\frac{ng/mL}{mg/kg}\right)$ | X.X | X.X | X.X | |
| | | X.X | X.X | X.X | |
| | , , | X.X | X.X | X.X | |
| | $C_{\text{trough}}\left(\frac{\text{ng/mL}}{\text{mg/kg}}\right)$ | X.X | X.X | X.X | |
| | | X.X | X.X | X.X | |
| | . , , | X.X | X.X | X.X | |
| | $AUC_{\tau}\left(\frac{ng \cdot hr/mL}{mg/kg}\right)$ | X.X | X.X | x.x | |
| | S. S | x.x | X.X | X.X | |

Table 30: Summary of Shift in T_{max} following Multiple Dosing

| | Median T | T _{max} (hr) | | 222/ 57 27 1 | | |
|---------------------|----------|-----------------------|----------------------------------|---|--|--|
| | Dose 1 | Dose 5 | Estimated Median Difference (hr) | 90% CI of Estimated Median Difference (hr) | | |
| Group 1 (3 mg/kg) | X.X | X.X | X.X | X.X, X.X | | |
| Group 2 (7.5 mg/kg) | X.X | X.X | X.X | X.X, X.X | | |
| Group 3 (15 mg/kg) | X.X | X.X | X.X | X.X, X.X | | |

Table 31: Statistical Analysis of Food Effect on Exposure

| Parameter | Fed GM | Fasted GM | Ratio (Fed / Fasted) | 90% CI of Ratio | CV _W (%) |
|----------------------|--------|-----------|-------------------------|-----------------|---------------------|
| AUC_{τ} | X.X | X.X | x.xxx | (x.xxx, x.xxx) | XX.XX |
| AUC _(0-∞) | X.X | X.X | x.xxx | (x.xxx, x.xxx) | xx.xx |
| C _{max} | X.X | X.X | x.xxx | (x.xxx, x.xxx) | XX.XX |

Table 32: Statistical Analysis of Food Effect on T_{max}

| | Fed Median | Fasted Median | Estimated Median Difference | 90% CI of Estimated Median Difference | Wilcoxon Signed Rank Test P-Value |
|------|------------|------------------|-----------------------------------|--|--------------------------------------|
| Tmax | X.X | X.X | x.xxx | (x.xxx, x.xxx) | x.xxx |

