| Subject ID | Treatment Group | $AR = \frac{AUC_{\tau,Dose 5}}{AUC_{\tau,Dose 1}}$ | $AR = \frac{C_{\text{max,Dose 5}}}{C_{\text{max,Dose 1}}}$ | $AR = \frac{1}{1 - e^{-\lambda_z \tau}}$ | Tmax, Dose 5 - Tmax, Dose 1 (hr) |
|------------|-----------------|--|--|--|----------------------------------|
| | | | | | |
| | | | | | |
| | | | | | |
| | | | | | |

Listing 5: Group 4 Subject Level Exposure Parameters

| | | AUC ₍ | $C_{(0-\infty)}$ (ng·hr/mL) | | AUC _(0-last) (ng·hr/mL) | | C _{max} (ng/mL) | | | T _{max} (hr) | | | |
|------------|----------|------------------|-----------------------------|-------------------------|------------------------------------|--------|--------------------------|-----|--------|-------------------------|-----|--------|------------------------------|
| Subject ID | Sequence | Fed | Fasted | Ratio Fed: Fasted | Fed | Fasted | Ratio Fed: Fasted | Fed | Fasted | Ratio Fed: Fasted | Fed | Fasted | Difference Fed- Fasted |
| | | | | | | | | | | | | | |
| | | | | | | | | | | | | | |
| | | | | | | | | | | | | | |
| | | | | | | | | | | | | | |

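### The Group 4 food-effect test is assigned two different partial AUCs, and the one in SAP 3.5.7 (AUClast) has no common end time in the two periods, which can inflate CVw and cost power

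*SAP*

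**What the plan says.** Five places bear on which partial AUC is tested alongside AUC0-inf and Cmax in Group 4.

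- Protocol 11.1 sets the 80-125% equivalence test on "AUC_{0-∞}, AUC₀₋₂₄, and C_{max} in accordance with FDA guidance".
- Protocol 11.4.4, for the same Group 4 confidence intervals, names "AUC to the time of the last quantifiable concentration" (AUC0-t).
- SAP 3.5.7: "Key exposure parameters (AUC_(0-∞), AUC_(0-last), and C_{max}) will be log-transformed and analyzed". The same parameter appears in "Listing 5: Group 4 Subject Level Exposure Parameters".
- "Table 31: Statistical Analysis of Food Effect on Exposure" is the shell for the SAP 3.5.7 results. Its rows are AUCtau, AUC0-inf and Cmax, with no AUClast row.
- SAP 3.4 says AUCtau "will be estimated for Dose 1 and Dose 5 in Groups 1, 2, and 3". It does not list it for Group 4.

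In SAP 3.4, tau "is the length of the dosing interval, 24 hours", so AUCtau and AUC0-24 are one quantity. AUC0-t and AUClast are the other: SAP 3.4 says AUClast "is defined as the AUC from dosing to the time of the last measured concentration" at or above the LLOQ in that dosing period. SAP 2.4 gives the LLOQ as 0.5 ng/mL, and SAP 3.1 treats late values below it as missing.

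**The concern.** The protocol disagrees with itself (11.1 against 11.4.4), so giving the SAP precedence does not settle which parameter is tested. Table 31 asks for a row that no Group 4 estimation step supplies. In an open-label study, an unresolved choice could be made after the concentrations are seen.

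The choice matters because AUClast has no fixed horizon. The Period 1 shell (SAP Table 12) stops at 24 h; the Period 2 shell (Table 13) adds 144 h. With Day 8 at +/-1 day and Day 14 at +/-2 days, the last sample can fall 72 to 216 h after the second dose. Whether the area after 24 h is counted in Period 2 depends on one sample near the LLOQ, subject by subject.

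Two planned results are exposed: the only comparison for which Protocol 11.2 states power, and CVw, which SAP 3.5.7 reports as an estimate of within-subject variability.

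**Working it through.** **1. The plan's own power.** Inputs from Protocol 11.2 and SAP 3.5.7: n = 12, 2x2 crossover, 90% CI within 0.80-1.25. The true ratio is not stated; 1.00 is assumed.

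sigma_w = sqrt(ln(1 + CV^2)); SE = sigma_w x sqrt(2/12); df = 10; the CI is the ratio multiplied and divided by exp(1.8125 x SE).

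| CV | sigma_w | SE | CI factor | Power | Protocol 11.2 |
|---|---|---|---|---|---|
| 0.175 | 0.1737 | 0.0709 | 1.137 | 79.9% | 80% |
| 0.20 | 0.1980 | 0.0809 | 1.158 | 64.4% | 64% |

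The stated figures reproduce.

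**2. Area at stake after 24 h.** Protocol 2.1.2 gives a half-life of 8.5-11 h and Tmax of 2 h. In a one-compartment oral model, the share of AUC0-inf within 24 h is 0.8509 at 8.5 h and 0.7712 at 11 h, so 15-23% lies later. The log-down rule recovers nearly all of that tail from a single quantifiable late sample. The Period 2 log shift is ln(1/0.8509) = 0.16 to ln(0.9999/0.7712) = 0.26.

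**3. Is Day 14 quantifiable?** Approximately, C(t) = Cmax x 2^(-(t-2)/t1/2). Over the whole Cmax range in Protocol 2.1.2 (about 944-6,768 ng/mL, all doses):

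- 72 h: 3.1-82 ng/mL
- 96 h: 0.44-18 ng/mL
- 144 h: 0.009-0.88 ng/mL

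The values straddle 0.5 ng/mL within the visit windows. At exactly 144 h, using the full one-compartment curve, a typical subject needs a Cmax of about 50,600, 15,100 or 3,700 ng/mL at half-lives of 8.5, 9.5 or 11 h. At nominal timing, quantifiable samples therefore come mainly from subjects with long half-lives. Early visits add more.

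**4. Effect on the residual.** If a fraction p of subjects gains a shift d in Period 2, the mean p x d goes into the period effect and the residual becomes MSE = sigma_w^2 + d^2 x p(1-p)/2. With sigma_w^2 = 0.03017 and p = 0.5:

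- d = 0.15: MSE = 0.03017 + 0.00281 = 0.03298; CVw = sqrt(exp(MSE) - 1) = 0.183; power 75%; CI factor 1.144.
- d = 0.25: MSE = 0.03017 + 0.00781 = 0.03798; CVw = 0.197; power 67%; CI factor 1.155.

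At p = 0 or p = 1 a uniform shift leaves CVw unchanged.

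**5. Simulation of the whole design.** Assumed: Cmax 1,000-3,500 ng/mL, between-subject half-life CV 10-20%, between-subject exposure CV 25%, assay noise 5%, 24-h draw uniform within +/-4 h, Day 8 and Day 14 visits exact or uniform within their windows. True within-subject CV is 17.5%, total exposure is equal, and Tmax is 2 h fed and fasted. Each scenario has 8,000 trials.

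| Tested AUC | t1/2 (h) | CVw | Power | Loss against AUC0-24 (points) |
|---|---|---|---|---|
| AUC0-24 | 8.5-11 | 17.5-17.8% | 78-81% | - |
| AUClast | 8.5 | 18.0-19.6% | 67-77% | 2-12 |
| AUClast | 9.5 | 18.1-20.9% | 59-77% | 4-20 |
| AUClast | 11 | 19.7-22.6% | 48-67% | 13-32 |

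With an assumed fed Tmax of 5 h, AUC0-24 power is 73-76%. AUClast gives 63-72%, 54-71% and 43-61% at the three half-lives.

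In a further 216 scenarios of 6,000 trials each, which also varied the Day 9 draw window, AUC0-24 was ahead in every one, by 1-32 points. Ending AUClast at the 24-h draw restored power to 75-79% (Tmax 2 h), so the Day 14 sample causes most of the loss.

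**The case against.** **AUClast is the dominant choice in the analysis text.** Protocol 11.4.4, SAP 3.4, SAP 3.5.7, Tables 22 and 25, Figures 16 and 20 and Listing 5 all use it. The exceptions are one hypothesis sentence and one empty shell, and SAP section 1 allows minor changes to table design. Correcting those two would remove the contradiction. That is true of the contradiction, but it would keep the parameter with the wandering end time, and deciding what is tested is more than table design.

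**The size depends on assumptions.** This stands. The documents give no Cmax at 3 mg/kg, no half-life spread and no visit-time distribution, and 8.5-11 h is a range over seven dose groups. With exact visits, 10% half-life spread and half-lives of 8.5-9.5 h, the loss is about 2-9 points. If the last sample falls 7 days after the second dose, as the follow-up in Protocol section 4 implies, it is 2-3 points in those cases. It stays large (15-26 points) at 11 h with 20% spread.

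**AUC0-24 has its own costs.** It omits 15-23% of total exposure at Tmax 2 h, and 18-26% of the fed profile at fed Tmax 5 h. In the latter case the fed/fasted ratio drops to 0.96-0.97 with equal total exposure. AUClast moves about as far, to 0.96-0.98. AUC0-24 also needs a rule, absent from the documents, for draws taken before 24 h.

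**A smaller change exists.** Dropping the Day 14 sample from AUClast comes within 1-5 points of AUC0-24. It is a reasonable fallback, though Protocol 11.1 and Table 31 would still need changing.

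**The stakes are limited.** Food effect is a secondary objective, and Protocol 11.4 calls the study exploratory. SAP 3.5.7 also plans residual diagnostics, but these are weak with 12 subjects.

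**Conclusion.** The concern holds and should be fixed before analysis. The contradiction needs no assumptions: two different quantities are assigned to one test, and Table 31 cannot be filled from the Group 4 parameters in SAP 3.4. The loss of precision is real but conditional. It requires a mix of subjects with and without a quantifiable Day 14 sample, or subject-to-subject differences in the area after 24 h. Under the Tmax 2 h assumptions, AUClast costs 2-32 points of power and moves CVw from about 17.5% to 18.0-22.6%. Confidence in the size is medium. The harm is a wider interval, an overstated CVw and a higher chance of failing to show equivalence. It is not a bias in the ratio from this source alone, nor a false claim of equivalence.

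**What to change.** - Make AUC0-24 the tested partial AUC in both periods, as Protocol 11.1 states, and keep AUC0-inf and Cmax as tested parameters.
- Align Protocol 11.4.4, SAP 3.5.7, Table 31 and Listing 5. Add AUC0-24 for Group 4 to SAP 3.4, using the Partial Area function already planned there.
- State one rule for both periods for draws taken before 24 h, for example log-linear extension from the last two samples.
- Reconcile the 24-h draw window: Protocol 7.6 gives +/-4 h on Day 2 and +/-2 h on Day 9, while Protocol Appendix A and SAP 2.3 give +/-4 h for both.
- Report AUClast descriptively; Tables 22 and 25 and Figures 16 and 20 can stay.
- Report AUC0-inf profiles that are non-estimable or more than 25% extrapolated, by period and condition, with a sensitivity analysis including the latter.

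The cost is small wording changes and one more noncompartmental parameter, with no new data. What remains unsolved is the tail beyond 24 h. AUC0-inf covers it only where lambda_z is acceptable and at most 25% is extrapolated. Under the same Tmax 2 h assumptions, AUC0-inf power is 67-77%, 53-68% and 26-34% at half-lives of 8.5, 9.5 and 11 h, and lower if food delays absorption. This change does not repair that.

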5. LISTING OF PROPOSED TABLES, FIGURES, AND LISTINGS

Proposed table, figure, and listing shells are presented in Appendices I, II, and III.

| Table 23: | Summary Statistics of PK Parameters by Group and Sex: Groups 1, 2 and 3, Dose 1 | 28 |
| Table 24: | Summary Statistics of PK Parameters by Group and Sex: Groups 1, 2 and 3, Dose 5 | 29 |
| Table 25: | Summary Statistics of PK Parameters by Group and Sex: Group 4 | 30 |
| Table 26: | Statistical Analysis of Attainment of Steady State | 31 |
| Table 27: | Population Summary Statistics for Accumulation Ratio | 32 |
| Table 28: | Dose Proportionality Power Model Estimates: Groups 1-3 | 33 |
| Table 29: | Geometric Mean Dose-adjusted Exposure by Dose Group | 34 |
| Table 30: | Summary of Shift in T _{max} following Multiple Dosing | 35 |
| Table 31: | Statistical Analysis of Food Effect on Exposure | 35 |
| Table 32: | Statistical Analysis of Food Effect on T _{max} | 35 |

Table 1: Summary of Demographic and Baseline Characteristics of Subjects Included in the Multiple Ascending Dose Trial PK Analysis

Note: Racial categories will be expanded as appropriate.

| Parameter | Group 1 (3 mg/kg) (N=) | Group 2 (7.5 mg/kg) (N=) | Group 3 (15 mg/kg) (N=) | All Groups (N=) |
|------------------------------|------------------------------|--------------------------------|-------------------------------|--------------------|
| Sex - N (%) | | | | |
| Male | x (x) | x (x) | x (x) | x (x) |
| Female | x (x) | x (x) | x (x) | x (x) |
| Age (Years) | | | | |
| Mean (SD) | x.x (x.x) | x.x (x.x) | x.x (x.x) | x.x (x.x) |
| Median | X.X | X.X | X.X | X.X |
| Min, Max | x, x | x, x | x, x | x, x |
| Height (cm) | | | | |
| Mean (SD) | x (x.x) | x (x.x) | x (x.x) | x (x.x) |
| Median | x | X | X | x |
| Min, Max | x, x | x, x | x, x | x, x |
| Weight (kg) | | | | |
| Mean (SD) | x.x (x.x) | x.x (x.x) | x.x (x.x) | x.x (x.x) |
| Median | X.X | X.X | X.X | X.X |
| Min, Max | x.x, x.x | x.x, x.x | X.X, X.X | x.x, x.x |
| BMI (kg/m²) | | | | |
| Mean (SD) | x.x (x.x) | x.x (x.x) | x.x (x.x) | x.x (x.x) |
| Median | X.X | X.X | x.x | X.X |
| Min, Max | x.x, x.x | x.x, x.x | x.x, x.x | X.X, X.X |
| Race – N (%) | | | | |
| Black or African American | x (x) | x (x) | x (x) | x (x) |
| White | x (x) | x (x) | x (x) | x (x) |

Table 2: Summary of Demographic and Baseline Characteristics of Subjects Included in the Food Effect Trial PK Analysis

Note: Racial categories will be expanded as appropriate.

| | Group 4, Sequence A | Group 4, Sequence B | All Groups |
|---------------------------|---------------------|------------------------|------------|
| Parameter | (N=) | (N=) | (N=) |
| Sex – N (%) | | | |
| Male | x (x) | x (x) | x (x) |
| Female | x (x) | x (x) | x (x) |
| Age (Years) | | | |
| Mean (SD) | x.x (x.x) | x.x (x.x) | x.x (x.x) |
| Median | X.X | X.X | X.X |
| Min, Max | x, x | x, x | x, x |
| Height (cm) | | | |
| Mean (SD) | x (x.x) | x (x.x) | x (x.x) |
| Median | X | X | X |
| Min, Max | x, x | x, x | X, X |
| Weight (kg) | | | |
| Mean (SD) | x.x (x.x) | x.x (x.x) | x.x (x.x) |
| Median | X.X | X.X | X.X |
| Min, Max | x.x, x.x | X.X, X.X | x.x, x.x |
| BMI (kg/m ²) | | | |
| Mean (SD) | x.x (x.x) | x.x (x.x) | x.x (x.x) |
| Median | X.X | x.x | x.x |
| Min, Max | X.X, X.X | X.X, X.X | x.x, x.x |
| Race – N (%) | | | |
| Black or African American | x (x) | x (x) | x (x) |
| White | x (x) | x (x) | x (x) |

Table 3: Individual Concentrations and Summary Statistics by Nominal Time: Group 1 (3 mg/kg), Dose 1

| | Nominal Time After Dose 1(hours) | | | | | | | | | | | | | |
|----------------|----------------------------------|--------|--------|--------|--------|--------|--------|--------|--------|--------|--|--|--|--|
| Subject ID | Pre-dose | 0.5 | 1 | 2 | 3 | 4 | 6 | 9 | 12 | 24 | | | | |
| 99ZZZ001 | Х | X | х | х | х | X | х | Х | Х | х | | | | |
| 99ZZZ002 | Х | X | Х | х | Х | х | Х | х | Х | х | | | | |
| 99ZZZ003 | Х | X | х | х | Х | х | Х | Х | Х | х | | | | |
| | Х | X | Х | х | Х | х | Х | х | Х | х | | | | |
| Statistic | | | | | | | | | | | | | | |
| N ¹ | Х | X | х | х | х | X | х | Х | Х | х | | | | |
| Mean | x.x | X.X | X.X | X.X | X.X | X.X | X.X | x.x | X.X | x.x | | | | |
| SD | x.x | X.X | X.X | X.X | x.x | X.X | x.x | x.x | x.x | x.x | | | | |
| GM | X.X | X.X | X.X | X.X | X.X | X.X | X.X | X.X | X.X | x.x | | | | |
| (Min, Max) | (x, x) | (x, x) | (x, x) | (x, x) | (x, x) | (x, x) | (x, x) | (x, x) | (x, x) | (x, x) | | | | |

¹ Number of data points used to compute the summary statistics. BQL values were imputed as 0 if they did not come after a PK sample concentration that is above the LLOQ and treated as missing otherwise.

Table 4: Individual Concentrations and Summary Statistics by Nominal Time: Group 2 (7.5 mg/kg), Dose 1

Table 5: Individual Concentrations and Summary Statistics by Nominal Time: Group 3 (15 mg/kg), Dose 1

Table 4 and **Table 5** will use the form of **Table 3** to display corresponding data for Groups 2 and 3.

Table 6: Individual Concentrations and Summary Statistics by Nominal Time: Group 1 (3 mg/kg), Dose 5

| | Nominal Time After Dose 5 (hours) | | | | | | | | | | | | | |
|------------|-----------------------------------|--------|--------|--------|--------|--------|--------|--------|--------|--------|--------|--------|--|--|
| Subject ID | Pre-dose | .5 | 1 | 2 | 3 | 4 | 6 | 9 | 12 | 24 | 72 | 120 | | |
| 99ZZZ001 | X | х | х | х | х | х | х | х | х | х | х | Х | | |
| 99ZZZ002 | X | х | х | х | Х | Х | х | х | х | х | х | х | | |
| 99ZZZ003 | X | Х | х | х | X | х | х | х | х | х | х | х | | |
| | X | Х | х | х | х | X | х | Х | х | х | х | Х | | |
| Statistic | | | | | | | | | | | | | | |
| N^1 | X | Х | Х | Х | Х | X | Х | Х | Х | х | х | х | | |
| Mean | X.X | X.X | x.x | x.x | x.x | x.x | X.X | X.X | x.x | x.x | x.x | X.X | | |
| SD | X.X | X.X | X.X | X.X | X.X | x.x | X.X | X.X | X.X | x.x | x.x | x.x | | |
| GM | X.X | X.X | x.x | x.x | x.x | x.x | X.X | X.X | x.x | x.x | x.x | x.x | | |
| (Min, Max) | (x, x) | (x, x) | (x, x) | (x, x) | (x, x) | (x, x) | (x, x) | (x, x) | (x, x) | (x, x) | (x, x) | (x, x) | | |

¹ Number of data points used to compute the summary statistics. BQL values were imputed as 0 if they did not come after a PK sample concentration that is above the LLOQ and treated as missing otherwise.

Table 7: Individual Concentrations and Summary Statistics by Nominal Time: Group 2 (7.5 mg/kg), Dose 5

Table 8: Individual Concentrations and Summary Statistics by Nominal Time: Group 3 (15 mg/kg), Dose 5

Table 7 and **Table 8** will use the form of **Table 6** to display corresponding data for Group 2 and Group 3.

Table 9: Peak and Trough Concentrations by Dose: Group 1 (3 mg/kg)

| | Dose 1 | | Dose 2 | | Dos | se 3 | Dos | se 4 | Dose 5 | |
|------------|-------------------|---------------------|--------|--------|--------|--------|--------|--------|--------|--------|
| | Peak ¹ | Trough ² | Peak | Trough | Peak | Trough | Peak | Trough | Peak | Trough |
| 99ZZZ001 | X | Х | X | X | X | Х | X | x | X | X |
| 99ZZZ002 | Х | х | Х | х | X | Х | Х | х | Х | х |
| 99ZZZ003 | X | Х | X | X | X | X | X | х | X | X |
| | X | Х | X | X | X | Х | X | х | X | X |
| Statistic | | | | | | | | | | |
| N^3 | X | X | X | X | X | X | X | X | X | X |
| Mean | x.x | x.x | x.x | X.X | x.x | X.X | X.X | X.X | X.X | X.X |
| SD | x.x | x.x | x.x | X.X | x.x | X.X | X.X | X.X | X.X | X.X |
| GM | x.x | x.x | x.x | x.x | x.x | x.x | X.X | X.X | X.X | X.X |
| (Min, Max) | (x, x) | (x, x) | (x, x) | (x, x) | (x, x) | (x, x) | (x, x) | (x, x) | (x, x) | (x, x) |

¹ Peak concentration is shown in this table as concentration at 2 hours (nominal time) after the corresponding dose.

Table 10: Peak and Trough Concentrations by Dose: Group 2 (7.5 mg/kg)

Table 11: Peak and Trough Concentrations by Dose: Group 3 (15 mg/kg)

Table 10 and **Table 11** will use the form of **Table 9** to display corresponding data for Group 2 and Group 3.

² Trough concentration is shown in this table as concentration at 24 hours (nominal time) after the corresponding dose.

³ Number of data points used to compute the summary statistics. BQL values were imputed as 0 if they did not come after a PK sample concentration that is above the LLOQ and treated as missing otherwise.

Table 12: Individual Concentrations and Summary Statistics by Nominal Time: Group 4 Sequence A, Period 1 (3mg/kg, Fasted)

| | | Nominal Time After Dose (hours) | | | | | | | | | | |
|------------|--------------|---------------------------------|--------|--------|--------|--------|--------|--------|--------|--------|--|--|
| Subject ID | Pre- dose | 0.5 | 1 | 2 | 3 | 4 | 6 | 9 | 12 | 24 | | |
| 99ZZZ001 | х | Х | Х | X | X | Х | X | X | X | X | | |
| 99ZZZ002 | х | Х | Х | X | X | Х | X | X | X | X | | |
| 99ZZZ003 | х | Х | Х | X | X | Х | X | X | X | X | | |
| | х | Х | Х | X | X | Х | X | Х | X | X | | |
| Statistic | | | | | | | | | | | | |
| N^1 | х | х | Х | Х | X | Х | Х | Х | X | X | | |
| Mean | x.x | X.X | X.X | x.x | x.x | X.X | x.x | x.x | X.X | X.X | | |
| SD | x.x | x.x | X.X | x.x | x.x | X.X | x.x | x.x | x.x | X.X | | |
| GM | x.x | X.X | X.X | X.X | X.X | X.X | X.X | X.X | X.X | X.X | | |
| (Min, Max) | (x, x) | (x, x) | (x, x) | (x, x) | (x, x) | (x, x) | (x, x) | (x, x) | (x, x) | (x, x) | | |

¹ Number of data points used to compute the summary statistics. BQL values were imputed as 0 if they did not come after a PK sample concentration that is above the LLOQ and treated as missing otherwise.

Table 13: Individual Concentrations and Summary Statistics by Nominal Time: Group 4 Sequence A, Period 2 (3mg/kg, Fed)

| | Nominal Time After Dose (hours) | | | | | | | | | | |
|------------|---------------------------------|--------|--------|--------|--------|--------|--------|--------|--------|--------|--------|
| Subject ID | Pre- dose | .5 | 1 | 2 | 3 | 4 | 6 | 9 | 12 | 24 | 144 |
| 99ZZZ001 | X | X | X | X | X | X | X | Х | X | Х | X |
| 99ZZZ002 | X | X | X | X | X | X | X | Х | X | Х | X |
| 99ZZZ003 | X | X | X | X | X | X | X | Х | X | Х | X |
| | X | X | X | X | X | X | X | Х | X | Х | X |
| Statistics | | | | | | | | | | | |
| N¹ | X | Х | X | X | Х | Х | Х | Х | X | Х | X |
| Mean | X.X | X.X | X.X | X.X | X.X | X.X | X.X | X.X | X.X | X.X | X.X |
| SD | x.x | x.x | X.X | x.x | x.x | x.x | X.X | x.x | X.X | X.X | X.X |
| GM | X.X | X.X | X.X | X.X | X.X | X.X | X.X | X.X | X.X | X.X | X.X |
| (Min, Max) | (x, x) | (x, x) | (x, x) | (x, x) | (x, x) | (x, x) | (x, x) | (x, x) | (x, x) | (x, x) | (x, x) |

¹ Number of data points used to compute the summary statistics. BQL values were imputed as 0 if they did not come after a PK sample concentration that is above the LLOQ and treated as missing otherwise.

Table 14: Individual Concentrations and Summary Statistics by Nominal Time: Group 4 Sequence B, Period 1 (3mg/kg, Fed)

Table 15: Individual Concentrations and Summary Statistics by Nominal Time: Group 4 Sequence B, Period 2 (3mg/kg, Fasted)

Table 14 and **Table 15** will use the forms of **Table 12** and **Table 13** to display corresponding data for Group 4, Sequence B.

Table 16: Individual PK Parameters and Summary Statistics: Group 1 (3 mg/kg), Dose 1

| | AUC_{τ} | Tmax | Cmax | Ctrough | λ_z | t _{1/2} |
|------------|--------------|------|---------|---------|---------------------|------------------|
| Subject ID | (ng·hr/mL) | (hr) | (ng/mL) | (ng/mL) | (hr ⁻¹) | (hr) |
| 99ZZZ001 | X | x.x | X | X | x.x | X.X |
| 99ZZZ002 | X | x.x | Х | х | X.X | X.X |
| 99ZZZ003 | х | x.x | Х | х | x.x | x.x |
| ••• | | | | | | |
| Statistic | | | | | | |
| N^1 | X | X | X | х | X | X |
| Mean | X.X | X.X | X.X | X.X | X.X | X.X |
| SD | X.X | x.x | X.X | X.X | X.X | X.X |
| Min | X | x.x | x | X | x.x | x.x |
| Median | Х | x.x | х | х | x.x | X.X |
| Max | X | x.x | x | х | x.x | x.x |
| CV % | X | x | x | х | X | X |
| GM | X.X | x.x | X.X | x.x | x.x | x.x |

¹ Number of data points used to compute the summary statistics. BQL values were imputed as 0 if they did not come after a PK sample concentration that is above the LLOQ and treated as missing otherwise.

Table 17: Individual PK Parameters and Summary Statistics: Group 1 (3 mg/kg),
Dose 5

| Subject ID | AUC _τ (ng·hr/mL) | AUC _{last} | T _{max} | C _{max} (ng/mL) | Ctrough | t _{1/2} | CL _{ss} /F |
|------------|-----------------------------|---------------------|------------------|--------------------------|---------|------------------|---------------------|
| 99ZZZ001 | | | ` ' | | | ì | |
| | X | X | X.X | X | X | X.X | X.X |
| 99ZZZ002 | X | X | X.X | X | X | X.X | X.X |
| 99ZZZ003 | X | X | X.X | X | X | X.X | X.X |
| | | | | | | | |
| Statistic | | | | | | | |
| N^1 | X | X | X | X | X | X | X |
| Mean | X.X | X.X | X.X | X.X | X.X | X.X | X.X |
| SD | X.X | X.X | X.X | X.X | X.X | X.X | X.X |
| Min | X | X | X.X | X | X | X.X | X |
| Median | X | X | X.X | X | X | X.X | X |
| Max | X | X | X.X | X | X | X.X | X |
| CV % | X | X | X | X | X | X | X |
| GM | X.X | X.X | X.X | X.X | X.X | X.X | X.X |

¹ Number of data points used to compute the summary statistics. BQL values were imputed as 0 if they did not come after a PK sample concentration that is above the LLOQ and treated as missing otherwise.

- Table 18: Individual PK Parameters and Summary Statistics: Group 2 (7.5 mg/kg),
 Dose 1
- Table 19: Individual PK Parameters and Summary Statistics: Group 2 (7.5 mg/kg), Dose 5
- Table 20: Individual PK Parameters and Summary Statistics: Group 3 (15 mg/kg),
 Dose 1
- Table 21: Individual PK Parameters and Summary Statistics: Group 3 (15 mg/kg), Dose 5

Table 18, Table 19, Table 20, and **Table 21** will use the forms of **Table 16 and Table 17** to display corresponding data for Groups 2 and 3.

Table 22: Individual PK Parameters and Summary Statistics: Group 4

| | A | UC _{last} | A | UC₀-∞ | - | T _{max} | | C _{max} | | t _{1/2} | (| CL/F | 1 | /d/F |
|------------|-----|--------------------|-----|----------|-----|------------------|-----|------------------|-----|------------------|-----|---------|-----|--------|
| Subject ID | (ng | g·hr/mL) | (ng | g·hr/mL) | | (hr) | (1 | ng/mL) | | (hr) | (I | /hr/kg) | (| (L/kg) |
| | Fed | Fasted | Fed | Fasted | Fed | Fasted | Fed | Fasted | Fed | Fasted | Fed | Fasted | Fed | Fasted |
| 99ZZZ001 | X | X | X | X | X.X | X.X | X | X | X.X | X.X | X.X | X.X | X.X | X.X |
| 99ZZZ002 | X | X | X | X | X.X | X.X | X | X | X.X | X.X | X.X | X.X | X.X | X.X |
| 99ZZZ003 | X | X | X | X | X.X | X.X | X | X | X.X | X.X | X.X | X.X | X.X | X.X |
| | | | | | | | | | | | | | | |
| Statistic | | | | | | | | | | | | | | |
| N^1 | X | X | X | X | X | X | X | X | X | X | X | X | X | X |
| Mean | X.X | X.X | X.X | X.X | X.X | X.X | X.X | X.X | X.X | X.X | X.X | X.X | X.X | X.X |
| SD | X.X | X.X | X.X | X.X | X.X | X.X | X.X | X.X | X.X | X.X | X.X | X.X | X.X | X.X |
| Min | X | X | X | X | X.X | X.X | X | X | X.X | X.X | X.X | X.X | X.X | X.X |
| Median | X | X | X | X | X.X | X.X | X | X | X.X | X.X | X.X | X.X | X.X | X.X |
